# 8.2. Primary Endpoint

The primary efficacy endpoint is the percentage of patients achieving an absolute SALT score of  $\leq 20$  at Week 24 (i.e., the binary endpoint denoting a SALT score  $\leq 20$ ).

#### 8.2.1. Computation of the Primary Endpoint

The SALT is a measure of hair loss that quantifies the amount of scalp surface without hair in a pre-specified quadrant of the scalp (right side, top, left side, back), that is further summed after applying a quadrant-specific multiplier indicative of scalp surface area contribution, to provide an overall score of total hair loss. A total SALT score equal to 0% indicates complete hair growth. A total SALT score equal to 100% indicates complete hair loss. An example of the SALT assessment can be found in Appendix 17.2 of protocol. The overall total SALT score is calculated in the eCOA system and will not re-derived. SALT scores are considered missing if the overall total could not be calculated. The primary endpoint is derived by categorizing the individual overall SALT scores at Week 24 ( $\leq 20$  versus > 20).

A multiple imputation (MI) approach will be used to estimate missing SALT scores.

One hundred independent imputations will be done with SAS® PROC MI using the Fully Conditional Specification (FCS) regression method. The FCS method combines both the monotone and arbitrary missing data patterns into one procedure, imputing missing values with a sequential regression approach.

For the primary efficacy analysis, missing SALT scores will be imputed under a missing at random (MAR) assumption. This assumes that patients who have missing data would have similar SALT scores as other patients in their respective treatment arm who have complete data. Any missing post-baseline SALT scores will be imputed to better inform the estimates of Week 24 missing SALT scores. Patients who have discontinued treatment but remain on study will not have their SALT scores censored, but any arbitrary missing SALT scores after the patient discontinued treatment will be imputed in the same manner. Utilizing the FCS method, missing

SALT scores will be imputed in a sequential manner using regression models with baseline SALT score and the observed or imputed values of previous visits as covariates. Imputations will be implemented separately for each treatment under the assumption that different treatments may have distinct posterior distributions.

In addition, prior to database lock, the classification of the missing data pattern for missing SALT scores will be finalized based on blinded data review and documented as either considered to be missing at random (MAR) or potentially missing not at random (MNAR), consistent with general categories of reasons for missingness. Subjects with missing data due to COVID-19 will have data reviewed to determine the specific limitation imposed by COVID-19 leading to the inability to have captured the protocol-specified assessments. For example, missing at random will be considered plausible for COVID-19 related reasons such as site closures and travel limitations. In general, however, if a MAR assumption is not considered plausible, MNAR will be assumed. Patterns of missing values across visits will be listed and summarized with numbers and percentages by treatment and visit.

Multiple imputation will be done using the Efficacy Population and will not be repeated separately for the Per Protocol Population. Multiple imputation will be repeated for the Modified Efficacy Population.

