## 10.2. Severity of Alopecia Tool (SALT)

The SALT score was introduced as part of investigative guidelines published by the National Alopecia Areata Foundation (Olsen, 2004). The SALT is a measure of hair loss that quantifies the amount of scalp surface without hair in a pre-specified quadrant of the scalp (right side, top, left side, back), that is further summed after applying a quadrant-specific multiplier indicative of scalp surface area contribution, to provide an overall score of total hair loss. The SALT assessment will occur via live examination of the patient during clinic visits. If a patient is unable to attend an in-person clinic visit due to COVID-19, a SALT assessment will not be performed. Missed assessments will be recorded in the eCRF as due to COVID-19.

SALT will be used to determine efficacy for the study. To reduce variability, one rater should perform the SALT assessment for the patient for the duration of the study. All investigators using the SALT will be trained prior to use. Please consult the associated Site Operations Manual for additional details regarding SALT scoring and training requirements for this study. An example of the SALT assessment tool is provided in Section 17.2.

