### **12.4.5.** Multiple Imputation

A multiple imputation (MI) approach will be used to estimate missing SALT scores. Analyses of the multiply imputed datasets will be performed for both the primary endpoint (percentage of subjects with absolute SALT scores  $\leq 20$ ) as well as key secondary endpoints employing SALT scores, between each dose and placebo, using the MMRM approach.

The imputation will be implemented separately for each treatment, under the assumption that different treatments may have distinct posterior distributions. Missing values will be imputed with a sequential regression approach under the assumption of multivariate normality. Missing SALT scores will be imputed in a sequential manner using regression models with a number of predictor variables. Covariates to be included are the baseline SALT score, in addition to the observed or imputed values of the previous time points.

One hundred independent imputations will be done with SAS® PROC MI using the Fully Conditional Specification (FCS) regression method for all imputed continuous variables and the discriminant function method for all imputed classification variables, if needed. For each continuous variable, all other variables are used as covariates, and for each imputed classification variable, all other continuous variables are used as covariates. The FCS method combines both the monotone and arbitrary missing data patterns into one procedure.

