#### 8.1.4. Multiple Comparisons/Multiplicity

Hierarchical testing will be used to control for multiple comparisons (Figure 1). For the primary efficacy analysis and the key secondary efficacy analyses, a  $\leq 0.025$  (two-sided) alpha-level will be allocated to each dose for comparison with placebo to adjust for multiplicity of testing associated with two doses. Once p>0.025 is observed for a treatment group comparison, inference for additional endpoints is no longer alpha-level protected for that dose group, however nominal p-values will still be reported.

Subsequently, conditional upon significance ( $\leq 0.025$ ) for the primary endpoint and first key secondary endpoint for each dose, a linear hierarchical testing approach with  $\leq 0.025$  (two-sided) alpha-level will be used to test the remaining key secondary endpoint comparisons versus placebo. Once p>0.025 is observed for a treatment group comparison, inference for additional endpoints is no longer alpha-level protected for that dose group; however, nominal p-values will still be reported.

All other statistical tests outside of the hierarchy will be carried out at a two-sided significance level of  $\leq 0.05$ . Nominal p-values will be presented without adjustment for multiple comparisons.

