#### Sensitivity 1: Multiple imputation; missing not at random (MNAR)

This sensitivity analysis is an implementation of a pattern mixture model that draws from different populations based on the reason for withdrawal from study. Patients who discontinued the study early due to a treatment-emergent adverse event (including COVID-19) or due to lack of efficacy will be considered MNAR. Treatment-emergent adverse event and lack of efficacy are reasons collected under "If 'Withdrew Consent', specify reason" on the *Study Discontinuation/Completion* eCRF page.

For patients who discontinued the study early due to a treatment-emergent adverse event or lack of efficacy, SALT scores missing after discontinuation will be imputed using the control arm. This assumes that patients, regardless of treatment, who discontinue the study early for those reasons would have similar SALT scores to placebo patients with complete data.

For patients who discontinued the study due to reasons other than treatment-emergent adverse event or lack of efficacy, missing SALT scores after subjects discontinue the study early will be multiply imputed from subjects within the same treatment group who have complete data at that time. Terms will include baseline values and the weekly data through the time point being imputed.

The proportion of patients who have a SALT score  $\leq 20$  will be calculated for each imputed dataset. The primary analysis, as described in Section 8.2.2, will be repeated for the Efficacy Population using the MI with MNAR assumption datasets.

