The next key secondary endpoints are the percentage of patients achieving an absolute SALT score of  $\leq 20$  (i.e., the binary endpoint denoting a SALT score  $\leq 20$ ) at Weeks 20, 16, 12, and 8. Missing data will be imputed according to Section 8.2.1. These endpoints will be assessed according to Section 8.2.2. If the primary endpoint and first key secondary endpoint are unsuccessful, nominal p-values for the SALT key secondary endpoints will be reported. This analysis will be completed for the Efficacy Population, the Per Protocol Population, and the Modified Efficacy Population. The Per Protocol Population will be considered supportive. The analysis utilizing the Modified Efficacy Population is considered a sensitivity analysis.

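### SAP 8.2.1 fills intermittent SALT gaps at Weeks 8–20 from earlier visits only, and keeps one of two covariate rules in Protocol 12.4.5 without recording the choice

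*SAP*

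**What the plan says.** **Method in the SAP.** SAP 8.2.1 specifies 100 imputations with PROC MI FCS, run separately by treatment under a missing-at-random (MAR) assumption. It describes the method this way: "The FCS method combines both the monotone and arbitrary missing data patterns into one procedure, imputing missing values with a sequential regression approach". The covariates it names are baseline SALT and earlier visits: "regression models with baseline SALT score and the observed or imputed values of previous visits as covariates". No PROC MI code is given.

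**Endpoints governed by that sentence.** For SALT ≤20 at Weeks 20, 16, 12 and 8, SAP 8.3.2 says: "Missing data will be imputed according to Section 8.2.1". SAP 8.1.4 places these endpoints in the hierarchy, where a two-sided 0.025 "alpha-level will be used to test the remaining key secondary endpoint comparisons versus placebo".

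**Protocol 12.4.5 contains two rules.** The second paragraph says: "Covariates to be included are the baseline SALT score, in addition to the observed or imputed values of the previous time points". The third, describing FCS, says: "For each continuous variable, all other variables are used as covariates".

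**Why gaps followed by observed visits are foreseeable.** Protocol 10.2 says: "If a patient is unable to attend an in-person clinic visit due to COVID-19, a SALT assessment will not be performed". Protocol 8.3 keeps patients who stop treatment in follow-up to Week 24, and SAP 8.2.1 itself expects arbitrary missing scores.

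**The concern.** MAR allows the chance that a score is missing to depend on any observed data, including scores observed later. An imputation model that uses only earlier visits needs a stronger condition: given baseline and earlier scores, the gap must be unrelated to what follows.

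Two things are at stake for the Week 8–20 responder rates:

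- **Precision.** The visit after a gap is among the best predictors of the missing score, and it is not used.
- **Possible bias.** If patients who later respond are more likely, or less likely, to have missed a visit, the imputed rate is pulled away from the true one.

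There is also a documentation point. SAP Section 13 itemises its edits to Protocol 12.4.5, down to removing the phrase on multivariate normality. It does not say that the all-other-variables rule was left out. SAP Section 2 gives the SAP primacy where the two documents differ, so the covariate set rests on one sentence.

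**Working it through.** The plan gives no figure on this point. Its power statement (>99% and about 92%) does not enter the argument; it reproduces at 99.9% and 92.5% with the continuity-corrected test.

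**Step 1: the texts side by side.**

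| Source | Covariates for a missing SALT score |
|---|---|
| Protocol 12.4.5, second paragraph | Baseline and previous time points |
| Protocol 12.4.5, third paragraph | All other variables, hence later visits too |
| SAP 8.2.1 | Baseline and previous visits |
| SAP 8.2.3, Sensitivity 1 | "Terms will include baseline values and the weekly data through the time point being imputed" |
| SAP Section 13 | No entry on this choice |

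The Sensitivity 1 wording fits the earlier-visits reading but is weak evidence for it. It concerns scores missing after study discontinuation, where no later score exists.

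**Step 2: precision.** Assume standardised normal scores with AR(1) correlation ρ between adjacent visits (0.80–0.95, not from the documents) and one gap visit. The residual SD of the imputation is √(1−ρ²) from the previous visit alone, and √[(1−ρ²)/(1+ρ²)] from both neighbours. The ratio is 1/√(1+ρ²).

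| ρ | Previous only | Both neighbours | Ratio |
|---|---|---|---|
| 0.80 | 0.600 | 0.469 | 0.78 |
| 0.90 | 0.436 | 0.324 | 0.74 |
| 0.95 | 0.312 | 0.226 | 0.72 |

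**Step 3: wrong status and bias.** Set the threshold so that 10%, 20% or 33% respond. *Wrong status* is the chance that a draw falls on the wrong side of the threshold. For bias, gaps are assumed twice as likely in patients who are responders at the next visit. The previous-only regression is fitted to the observed cases, and the arm's rate combines observed and imputed status.

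| ρ | Rate | Wrong status, previous only → both | Bias in points, previous only, at 2% / 5% / 10% gaps |
|---|---|---|---|
| 0.80 | 10% | 11.6% → 9.1% | −0.04 / −0.11 / −0.23 |
| 0.80 | 20% | 19.1% → 14.9% | −0.07 / −0.18 / −0.37 |
| 0.80 | 33% | 25.2% → 19.5% | −0.08 / −0.22 / −0.45 |
| 0.90 | 10% | 8.5% → 6.3% | −0.04 / −0.09 / −0.19 |
| 0.90 | 20% | 13.8% → 10.2% | −0.05 / −0.14 / −0.29 |
| 0.90 | 33% | 18.1% → 13.4% | −0.07 / −0.17 / −0.35 |
| 0.95 | 10% | 6.1% → 4.4% | −0.03 / −0.07 / −0.14 |
| 0.95 | 20% | 9.9% → 7.1% | −0.04 / −0.10 / −0.21 |
| 0.95 | 33% | 12.9% → 9.3% | −0.05 / −0.12 / −0.25 |

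I repeated the 10% and 33% rows with 1,000,000 draws. The biases agreed to within 0.01 points, and adding the later score brought every one to 0.00. With gaps half as likely in later responders the sign reverses (+0.02 to +0.36). With gaps completely at random the bias is 0.00 either way, and only precision is lost.

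In patients, the largest value is 0.45% × 110 = 0.5 of a patient in a 110-patient arm, or 0.45% × 220 = 1.0 in the 8 mg arm. If the same mechanism acts on placebo, part of it cancels: at ρ = 0.80 and 10% gaps, a 33% arm against a 10% arm gives −0.45 − (−0.23) = −0.22 points on the difference.

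A separate finite-sample check used arms of 110, ρ = 0.9 and 4–10% gaps that depended on the Week 24 outcome. All-visit imputation lowered the error (RMSE) at Week 20 by about 7–14% and cut the bias from −0.6 to −0.2 points. That is slightly above the table's range but of the same order.

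**Step 4: Week 24.** No SALT is scheduled after Week 24, so its own imputation model loses no later score. There is a second-order effect. If 4% or 10% of Week 20 scores are filled without Week 24, the Week 20 slope in the Week 24 regression falls by about 4% or 10%, and the residual SD rises by about 3–8%. This reaches only patients whose Week 24 score is itself missing.

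**The case against.** The strongest case against rests on four points.

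- **The SAP follows the protocol.** A reader might infer that the SAP departs from it. The documents do not support that: the SAP's covariate sentence closely matches the SALT-specific rule in Protocol 12.4.5. The inconsistency lies inside the protocol, and the SAP resolves it silently in one direction. What remains is that the choice is unrecorded and is the less efficient of the two.
- **The SAP names FCS for arbitrary patterns.** A reader might infer that the method is not FCS at all, or cannot handle intermittent gaps. That is too strong. Missing scores do get imputed, and without code the model that will be run is not certain. Earlier visits only is the literal reading, and the text should settle it.
- **The size is negligible.** This largely stands. In a trajectory simulation with linear draws and 4% gaps, wrong Week 20 status in the 12 mg arm fell from 10.3% to 8.3%. With 110 × 4% = 4.4 gap patients, that is 4.4 × 2% = 0.09 of a patient. Whole-arm rates moved by about 0.2 points or less.
- **No inferential consequence is shown.** This also stands. Nothing here shows a change in Type I error, in power or in the outcome of the hierarchy. Bias needs gaps that track later response. Site closures and travel limits, the examples that SAP 8.2.1 gives as plausibly MAR, need not do so.

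Nor does an imputed path that dips and recovers count against the plan. Protocol 4.1 describes unpredictable loss and regrowth.

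**Conclusion.** The point holds as a small improvement in method and a gap in documentation. As written, SAP 8.2.1 leaves observed later scores out of the imputation of intermittent gaps in four alpha-controlled endpoints, and Section 13 does not say that one of two protocol rules was set aside.

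The cost is some precision. If gaps relate to later response, there is also a bias of about 0.5 points per arm or less (0.6 at most in the finite-sample check). These sizes rest on assumed gap rates of 2–10%, correlations of 0.80–0.95, a normal AR(1) model and a two-to-one dependence of gaps on later response in the main table. None of these is in the documents.

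A reader might infer that the primary result is in doubt. It is not: Week 24 is the last scheduled SALT visit, and the indirect effect reaches only patients missing that visit. A changed conclusion at Weeks 8–20 is also unlikely. Label: free improvement.

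**What to change.** In SAP 8.2.1, state that each FCS regression for SALT uses baseline SALT and all other scheduled SALT visits, earlier and later, within treatment arm, and give the PROC MI code. In Section 13, add an entry under Protocol 12.4.5 saying that this resolves its two covariate rules. If the sponsor prefers earlier visits only, the SAP should say so and give the reason.

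The cost is a few lines of text and one model statement before database lock. No new data are needed, and the endpoints, tests and alpha allocation stay as they are.

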#### 8.2.2. Primary Analysis of the Primary Endpoint

Pairwise treatment group differences from placebo will be assessed with the Mantel-Haenszel test (common risk difference) using baseline scalp hair loss (partial vs complete/near-complete) as the stratification factor, for each active treatment group versus placebo.

For each imputed dataset, treatment differences will be assessed using the Mantel-Haenszel estimate of a common risk difference, with the variance estimator (used to construct confidence limits for the Mantel-Haenszel estimate of the common risk difference in the SAS FREQ Procedure). The resulting 100 estimates of the treatment differences and standard errors will then be combined using SAS PROC MIANALYZE. The following SAS options for PROC FREQ will be used to estimate a common risk difference, confidence intervals, and p-values by imputation for placebo compared to each dose separately:

proc freq data = <>;
by IMPUTATION;
tables STRATA\*TREATMENT\*RESPONSE / commonriskdiff(cl=mh test=mh);
run;

The observed number and percentage of patients with an absolute SALT score  $\leq 20$  among nonimputed data will be reported by treatment group along with the appropriate p-value, the combined treatment differences, combined standard errors, and 95% confidence intervals (CI). This analysis will be completed for the Efficacy Population and the Per Protocol Population. The analysis utilizing the Per Protocol Population is considered supportive. The results may also be displayed graphically.

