## 12.4.5.1. Analysis of Imputed Datasets

For the analysis of the primary endpoint (i.e., the binary endpoint denoting a SALT score  $\leq$  20) the individual SALT scores will be categorized ( $\leq$  20 versus > 20) and analyzed using a Mantel-Haenszel test (comparing each dose to placebo, separately). For each imputed dataset, treatment differences will be assessed using the Mantel-Haenszel estimate of a common risk difference, with the variance estimator due to Sato (used to construct confidence limits for the Mantel-Haenszel estimate of the common risk difference in the SAS FREQ Procedure). The resulting 100 estimates of the treatment differences and standard errors will then be combined using SAS PROC MIANALYZE.

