Results of statistical models (ie, least-squares means, confidence intervals, risk differences) will be rounded to one additional decimal place from the original data, or a maximum of two decimal places. Standard error will be reported to an additional level of precision. Results which cannot be determined will be displayed as "NA", "NE", or similar.

For tests of hypothesis of treatment group differences, the associated p-value will be reported. All p-values will be rounded to four decimal places after assignment of statistical significance; pvalues that round to 0.0000 or are reported by SAS as zero will be presented as "≤0.0001"; pvalues that round to 1 or are reported by SAS as 1 will be presented as ">0.9999". P-values which are significant at a 0.05, 0.025, 0.01, 0.001, or 0.0001 level will be marked with asterisks. P-values which cannot be determined will be displayed as "NA". P-values are descriptive for outcomes and analyses not included in the multiplicity algorithm.

Date of last dose is collected on the *Treatment Discontinuation/Completion* eCRF page. For patients with missing or partial date of last dose, the date of last dose (ie, treatment end date) will be imputed. Date of last dose will be imputed as follows:

- Derive the number of tablets taken at the last visit as the dispensed amount minus the returned amount. For treatment compliance (Section 7.3) and exposure (Section 9.2), if the returned amount is missing, it will be assumed that zero tablets were taken. Otherwise, it will be assumed that 60 tables were taken.
- An estimated date of possible last dose will be calculated by adding the number of tablets taken divided by 2 to the visit date associated with the last visit where drug accountability was collected.
- If there is a partial date of last dose, missing day will be imputed using the day from treatment start date, or the last day of the month if that month has fewer days than the treatment start month.
- Treatment end date will be the minimum of the partial date of last dose, calculated estimated date of possible last dose, and collected study discontinuation/completion date.

Summary tables and data listings:

- Unless otherwise specified, no preliminary rounding will be performed; rounding will only occur after analysis.
- Data from patients excluded from an analysis population will be presented in the data listings but will not be included in the calculation of summary statistics, where applicable.

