- Data from each patient will be separated by a blank line. Within a data listing, if a descriptive item appears line after line (e.g., repetition of a patient number, date, visit, etc.), only the first occurrence will be displayed (e.g., in Listing of Vital Signs, patient number, date and visit will only be displayed on first row when presenting all parameters collected at same visit). Repetition of actual results or outcomes (e.g., adverse events, lab results, vital sign values, etc.) will not be collapsed.
- Data listings will be sorted by treatment, patient, and date and/or time of assessment, as applicable.
- When change from baseline or change to baseline is calculated, baseline is the last observation obtained prior to first dosing of the study drug.
- Unless otherwise noted, values reported as greater than or less than some quantifiable limit (e.g., "< 2.0") will be summarized as using the numeric equivalent in summary tables and figures (e.g. "<2.0" will be analyzed as 2.0). The reported value will be used in listings.

Mock tables and data listings will be provided as attachments to this analysis plan. Minor changes to the mocks after formal SAP approval will not necessitate re-approval unless changes to the text of the SAP are required.

All statistical deliverables will be produced, validated, and reviewed for accuracy/consistency in accordance with standard operating procedures and the processes described in the statistical validation plan.

SAS® (SAS Institute, Cary, North Carolina) statistical software, version 9.4 or later, will be used for all analyses. Adverse Events and Medical History will be coded in Medical Dictionary for Regulatory Activities (MedDRA) Version 23.1. Concomitant medications will be coded in World Health Organization (WHO) Drug Version 2020-SEP and Anatomical-Therapeutic-Chemical (ATC) classification and preferred term.

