#### **Figure 1: Hierarchical Testing**

#### 8.3.1. Satisfaction of Hair Patient Reported Outcome (SPRO) at Week 24

The first key secondary endpoint is the percentage of responders per the SPRO at Week 24. The SPRO is a single item questionnaire answered by the patient, designed to measure how satisfied alopecia areata patients are with their hair at the time of the assessment. The SPRO responses are on a scale of 1-5, where 1 = very satisfied, 2 = satisfied, 3 = neither satisfied nor dissatisfied, 4 = dissatisfied, and 5 = very dissatisfied. An example of the SPRO assessment can be found in Appendix 17.4.1 of the protocol.

A responder is defined as patients with answers of "very satisfied" or "satisfied" at Week 24 on the SPRO. This endpoint will be assessed similar to the primary analysis of the primary endpoint, according to Section 8.2.2.

Missing data will be imputed similarly to the primary endpoint according to Section 8.2.1. However, since the SPRO scale is ordinal, the FCS logistic regression method will be used in lieu of the FCS regression method. The missing SPRO scores will be imputed in a sequential manner using logistic regression models with baseline SALT score, baseline SPRO score, and the observed or imputed SPRO values of previous visits as covariates.

The observed number and percentage of SPRO responders by treatment group will be reported along with the appropriate p-values. Both CTP-543 doses will be tested in parallel against placebo with a  $\leq 0.025$  alpha level. This analysis will be completed for the Efficacy Population, the Per Protocol Population, and the Modified Efficacy Population. The Per Protocol Population will be considered supportive. The analysis utilizing the Modified Efficacy Population is considered a sensitivity analysis. If the primary endpoint is unsuccessful, nominal p-values will be reported.

#### 8.3.2. SALT Score ≤ 20 at Weeks 20, 16, 12, and 8

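### Does showing 95% confidence intervals for the primary risk differences conflict with testing each dose at two-sided 0.025?

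*SAP*

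**What the plan says.** SAP 8.1.4 divides the overall two-sided 0.05 between the doses. For the primary and key secondary analyses, a two-sided 0.025 "alpha-level will be allocated to each dose for comparison with placebo to adjust for multiplicity of testing associated with two doses". If a comparison gives p>0.025, "inference for additional endpoints is no longer alpha-level protected for that dose group", although nominal p-values are still reported. Protocol 12.4.2 and 12.4.3 set the same level, and the sample size in Protocol 12.1 is calculated at it.

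SAP 8.2.2 estimates a Mantel-Haenszel common risk difference in each of 100 imputed datasets, stratified by extent of scalp hair loss. The SAS options request Mantel-Haenszel limits and a Mantel-Haenszel test. Protocol 12.4.5.1 describes the same estimator "with the variance estimator due to Sato". The estimates and standard errors are then pooled in PROC MIANALYZE. The display gives the observed response counts, the p-value, and "the combined treatment differences, combined standard errors, and 95% confidence intervals (CI".

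Two conventions in SAP 4 bear on how the table will be read. One is "P-values which are significant at a 0.05, 0.025, 0.01, 0.001, or 0.0001 level will be marked with asterisks". The other is "Mock tables and data listings will be provided as attachments to this analysis plan"; those shells are not part of the public documents.

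The key secondary endpoints follow the same method by reference: for satisfaction with hair (SAP 8.3.1), "This endpoint will be assessed similar to the primary analysis of the primary endpoint, according to Section 8.2.2"; for SALT ≤20 at earlier weeks (SAP 8.3.2), "These endpoints will be assessed according to Section 8.2.2". Neither section names an interval level of its own.

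**The concern.** A confidence interval is usually read as the set of differences that the test would not reject. A 95% interval matches a test at 0.05, but here each dose is tested at 0.025. The plan adjusts the test for two doses and leaves the interval unadjusted. By the Bonferroni inequality, two 95% intervals jointly cover both true differences with probability of at least 1 − 2 × 0.05 = 90%. Two 97.5% intervals would guarantee at least 1 − 2 × 0.025 = 95%.

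The two levels can give visibly different messages. For 0.025 < p < 0.05 the interval excludes zero and the comparison fails. (At p = 0.05 exactly, the limit sits on zero.) No visible passage calls the primary interval nominal, although SAP 4 and 8.1.4 do say so of p-values outside the hierarchy. SAP 8.2.2 also allows a graphical display, where an interval might be seen without its p-value. At stake is a borderline primary result being read as a success.

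**Working it through.** **Inputs.** Group sizes of 110 (12 mg), 220 (8 mg) and 110 (placebo), response rates of 40%, 26% and 9%, and two-sided 0.025 per dose all come from Protocol 12.1. The 95% level comes from SAP 8.2.2. The normal multipliers are 1.960 for 95% and 2.241 for 97.5%.

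**1. The plan's own power figure.** With a continuity correction c = ½(1/n₁ + 1/n₀), power = Φ[(d − c − 2.241·SE₀)/SE₁], where SE₀ uses the pooled rate and SE₁ the separate rates.

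- 8 mg: d = 0.17, c = 0.0068, pooled rate (0.26·220 + 0.09·110)/330 = 0.2033, SE₀ = 0.0470, SE₁ = 0.0402. Power = Φ(1.44) = 92.5%.
- 12 mg: d = 0.31, c = 0.0091, pooled rate 0.245, SE₀ = 0.0580, SE₁ = 0.0541. Power = Φ(3.16) = 99.9%.

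These match the stated figures of about 92% and >99%. At 0.05 the 8 mg power would be 96.1%, so 0.025 is the operative level.

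**2. When test and interval part company.** If both come from the same pooled estimate and standard error, the 95% interval excludes zero when |d|/SE > 1.960 and the test succeeds when |d|/SE ≥ 2.241. They disagree only between those values, that is, for 0.025 < p < 0.05. The width ratio is 2.241/1.960 = 1.144.

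**3. An example (invented counts, unstratified Wald).** For 8 mg 38/220 and placebo 10/110, d = 8.18 points, SE = 3.74 and p = 0.029. The 95% CI is 0.8 to 15.5 and the 97.5% CI is −0.2 to 16.6, so the two disagree.

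With the planned stratification and the Sato variance, the answer depends on the assumed strata:

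| Assumed strata (8 mg; placebo) | Total, 8 mg | p | 95% CI | 97.5% CI |
|---|---|---|---|---|
| 60:40 (30/132, 8/88; 8/66, 2/44) | 38/220 | 0.027 | 0.9 to 15.4 | −0.1 to 16.5 |
| 50:50 (30/110, 8/110; 8/55, 2/55) | 38/220 | 0.0247 | 1.0 to 15.3 | 0.0 to 16.3 (lower limit 0.02) |
| 50:50 (29/110, 8/110; 8/55, 2/55) | 37/220 | 0.033 | 0.6 to 14.8 | −0.4 to 15.9 |

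Rows 1 and 3 disagree with the test; row 2 does not.

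**4. Which observed differences are affected.** Solve d = z·√[(p₀+d)(1−p₀−d)/n + p₀(1−p₀)/110] at z = 1.960 and z = 2.241, with n the size of the active arm. The band depends on the observed placebo rate p₀:

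| Placebo rate (assumed) | 8 mg, points | 12 mg, points |
|---|---|---|
| 5% | 5.8 to 6.7 | 7.4 to 8.7 |
| 9% | 7.2 to 8.4 | 8.9 to 10.4 |
| 13% | 8.3 to 9.6 | 10.1 to 11.7 |

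**5. How likely it is.** At the planned rates, P = Φ(2.241 − d/SE) − Φ(1.960 − d/SE).

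- 8 mg: d/SE = 0.17/0.0402 = 4.22, so 0.0237 − 0.0118 = 0.0119, about 1.2%.
- 12 mg: d/SE = 0.31/0.0541 = 5.73, so 0.00024 − 0.00008 = 0.00016, about 0.02%.
- No effect: 0.05 − 0.025 = 2.5% per dose, half of it (1.25%) favouring active treatment.

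**6. What the other level would print.** For 8 mg at the planned effect, the 95% CI is 17.0 ± 7.9, or 9.1 to 24.9 points; the 97.5% CI is 17.0 ± 9.0, or 8.0 to 26.0.

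**The case for a change.** The best case for a change is that the plan is careful to label p-values that lack multiplicity protection but leaves the primary interval unlabelled, and that a reporting rule is best settled before unblinding. The cost would be small: one alpha option in PROC MIANALYZE, or one footnote. If the 8 mg effect were smaller than planned, a result in the band would be likelier than 1.2%, and the difference in level exists whatever the result.

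Much of this stands as description. The interval is not adjusted for two doses, and a borderline result would need care in reading. It does not show a fault in the plan. A 95% interval that is stated to be 95% is labelled correctly; it simply answers the estimation question for one dose at a time. SAP 8.4 uses 95% intervals for the continuous secondary endpoints too, so this is the SAP's usual reporting level. The asterisk convention in SAP 4 separates 0.025 from 0.05, and the p-value is reported with the interval. Whether a nominal label is absent cannot be established without the table shells.

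Nor would 97.5% intervals settle every reading problem. For the key secondary endpoints, protection depends on all earlier steps for that dose, and no interval level conveys that.

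**Conclusion.** No change to the plan is called for. SAP 8.1.4 defines success by p ≤ 0.025 per dose, and neither document gives the interval a part in that decision. Following the plan as written yields a valid test at the intended level and a correctly stated 95% interval. Type I error, power and sample size do not depend on which interval is printed.

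The point is confined to presentation of the primary endpoint when 0.025 < p < 0.05. Its chance is about 1.2% (8 mg) and 0.02% (12 mg) at the planned effects, and 2.5% per dose if there is no effect. These figures assume unstratified Wald intervals, the planned group sizes and no missing data; multiple imputation is not modelled. The relation in step 2 needs only that p-value and interval share one pooled estimate and standard error. SAP 8.2.2 supports that reading, although it does not spell out the source of the p-value.

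Choosing between 95% and 97.5% intervals beside an adjusted test is a matter on which reasonable statisticians differ. Analysts who want to head off misreading can note on the output that the intervals are not adjusted for multiplicity; that needs no amendment.
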